### **12.9.2 Local Tolerability Scale (LTS)**

LTS scores will be summarized by treatment and visit for subject overall assessment (scores from 0=None to 4=Strong/Severe) and Investigator overall assessment (scores from 0=No irritation to 4=Very Severe) separately. LTS scores at the sensitive areas will be summarized by visit, area and treatment group for Investigator overall assessment, as well as listed by subject and anatomical site.

### **12.9.3 Clinical Laboratory Testing**

All clinical laboratory (hematology, clinical chemistry, urinalysis) values will be listed by subject. The reference normal ranges and reference range indicators (e.g. high, low, normal etc.) will be supplied by the central laboratory and displayed in the data listings. For the purpose of shift table summaries, the central lab reported reference range indicators will be classified as low, normal and high accordingly based on the table below. Change from baseline in abnormality status will be summarized using shift tables. For urinalysis, only lab tests with numeric results reported are included in shift tables. Separate listings will identify subjects with markedly abnormal values. For quantitative measures, observed values and changes in clinical laboratory values will be summarized descriptively by visit and treatment group.

Reference Range Indicator in Shift Tables	Reference Range Indicator Reported by Central Lab
Low	Low, Low Level 1 Alert, Low Level 2 Alert
Normal	Normal
High	High, High Level 1 Alert, High Level 2 Alert

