1.3.1.2. Systemic Adverse Events

Nasopharyngitis and headache were the most frequently-reported nondermatological AEs in dose-ranging Study 203120 in psoriasis. In dose-ranging Study 203121 in AD, the most frequently reported nondermatological AEs were nasopharyngitis, upper respiratory tract infection, and headache. In the initial clinical studies (in AD and psoriasis) using a different tapinarof formulation (Formulation C), nasopharyngitis, and headache were the most frequently reported nondermatological AEs. In the open-label PK Study 201851 with BID dosing of Formulation F of tapinarof cream (n=11), 1% and 2%, headache was the most frequently reported during the study (reported for 100% and 60% of subjects at the 1% and 2% doses, respectively).

In a nonclinical study in minipigs using intravenous (IV) administration, reversible decreases in arterial blood pressure and PR interval were observed; however, in this study and repeat dermal toxicity studies, there were no effects on QT interval or heart rate. Repeat-dose dermal toxicity studies also showed findings related to the liver (increased weights and hepatocellular hypertrophy/regeneration) and thymus (thymic cortex depletion in adult rabbits and rats; changes in thymus weight, microscopic decreased cellularity, and changes in thymic T cell maturation in juvenile rats) with associated secondary hematological findings. Thymic findings were also noted in repeat adult and juvenile rat studies; however, there were no clinically relevant AEs/serious adverse events (SAEs) reported.

To mitigate potential systemic risks, subjects will be monitored for AEs and any abnormal vital signs, physical examination, and laboratory test results.

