
 To describe the effect of tapinarof cream, 1% on psoriasis symptom severity and the associated impact on daily activities and attitudes in adults with plaque psoriasis 	
 Change in Peak Pruritus-Numeric Rating Scale (Peak Pruritus-NRS) from Baseline at Weeks 2, 4, 8, and 12 Change over time in psoriasis impact on daily activities, as measured by the Dermatology Life Quality Index (DLQI) total and individual dimension scores Change over time in psoriasis symptoms, as measured by the Psoriasis Symptom Diary (PSD) Change over time in physical component score and mental component score, as measured by the Short Form-36 (SF-36) questionnaire

 To evaluate the safety and tolerability of tapinarof cream, 1% 	
Safety:
 
 Incidence, frequency, and duration of treatment emergent adverse events (TEAEs) and serious adverse events (SAEs)

Objectives	Associated Endpoint
in adults with plaque psoriasis	
• Clinically significant change from Baseline in laboratory values• Clinically significant change from Baseline in vital signs• Mean Local Tolerability Scale (LTS) scores by visit

• To characterize the PK of tapinarof in adults with plaque psoriasis	Pharmacokinetic: 
• Plasma concentration of tapinarof at Weeks 4 and 12

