4.3. Exclusion Criteria

A subject who meets any of the following criteria will be excluded and considered ineligible for participation in the study:

1. Psoriasis other than plaque variant
2. Any sign of infection of any of the psoriatic lesions
3. Concurrent conditions or history of other diseases:
 - a. Immunocompromised (eg, lymphoma, acquired immunodeficiency syndrome) or medical history of positive human immunodeficiency virus (HIV) antibody at Screening
 - b. Chronic or acute systemic infection requiring treatment with systemic antibiotics, antivirals, antiparasitics, antiprotozoals, or antifungals within 4 weeks prior to the Baseline visit
 - c. Acute active bacterial, fungal, or viral (herpes simplex, herpes zoster, chicken pox) skin infection within 1 week prior to the Baseline visit
 - d. Significant dermatologic or inflammatory condition other than plaque psoriasis that, in the Investigator's opinion, would make it difficult to interpret data or assessments during the study
4. Screening alanine aminotransferase (ALT) or aspartate aminotransferase (AST) $\geq 1.5x$ the upper limit of normal (ULN)
5. Screening total bilirubin $> 1.5 x$ ULN; total bilirubin $> ULN$ and $\leq 1.5 x$ ULN is acceptable if bilirubin is fractionated and direct bilirubin $< 35\%$.
6. Corrected QT (QTcF) interval > 475 msec.
7. Current or chronic history of liver disease, known hepatic or biliary abnormalities (with the exception of Gilbert's syndrome or asymptomatic gallstones), presence of hepatitis B surface antigen (HBsAg), or positive hepatitis C antibody test result, or a positive anti-hepatitis B core antigen (anti-HBc) result. Subjects with a history of HCV infection who were medically cured and have an undetectable viral load are eligible to enroll. Subjects with a history of stable non-alcoholic fatty liver disease without evidence of active inflammation (elevated ALT/AST $\geq 1.5x$ ULN) or cirrhosis are eligible to enroll.
8. Ultraviolet (UV) light therapy or prolonged exposure to natural or artificial sources of UV radiation (eg, phototherapy, tanning beds/booths, or therapeutic sunbathing) within

- 4 weeks prior to the Baseline visit and/or plans to have such exposures during the study which could potentially impact the subject's psoriasis (as determined by the Investigator).
9. Use of any prohibited medication within the indicated period before the Baseline visit.

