### **11.3 Baseline and Change from Baseline**

Baseline value is defined as the last non-missing value prior to the first dose of study drug. Change from baseline is defined as the post-baseline value minus the baseline value unless otherwise specified. Percent change from baseline is calculated as follows: Percent change = (Change from baseline / Baseline) \* 100.

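### SAP 12.9.3 merges High with both alert levels in the laboratory shift tables, so no planned laboratory table counts alert-level worsening by arm, including in subjects admitted above ULN

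*SAP*

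**What the plan says.** SAP 12.9.3 has the central laboratory supply a range indicator with each result, then reduces the indicators for tabulation: "For the purpose of shift table summaries, the central lab reported reference range indicators will be classified as low, normal and high accordingly". In the mapping table, High takes in "High, High Level 1 Alert, High Level 2 Alert", Low takes in its three counterparts, and Normal stands alone. Change in abnormality status from baseline is then shown in shift tables. The same section lists all values with their indicators, lists subjects with markedly abnormal values separately, and summarizes values and changes by visit and arm.

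On who can enter, Protocol 4.3 excludes ALT or AST at or above 1.5x ULN (criterion 4). Under criterion 5, total bilirubin above ULN and up to 1.5x ULN "is acceptable if bilirubin is fractionated and direct bilirubin" is below 35%. Criterion 7 makes an allowance for "Subjects with a history of stable non-alcoholic fatty liver disease without evidence of active inflammation" or cirrhosis.

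Protocol Section 2 lists as a safety endpoint "Clinically significant change from Baseline in laboratory values". Protocol 1.3.1.2 gives a reason to look at the liver: "Repeat-dose dermal toxicity studies also showed findings related to the liver".

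**The concern.** A shift table is the usual place to see, by arm, how many subjects moved to a worse laboratory status. With three categories it has no room above High. A subject who starts above ULN on a test therefore cannot be shown as worsening on that test, whatever the later result. Among subjects who start Normal, a result just over the limit and one that triggers the laboratory's highest alert are counted alike.

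At stake is how well the report can compare the arms on large laboratory changes. The nonclinical liver findings make ALT, AST and bilirubin the tests where this matters most. They are also the tests for which eligibility expressly allows values above normal.

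**Working it through.** The plan states no figure on this point, so there is none to reproduce. The check applies the SAP mapping to each possible upward move and then looks at what the other outputs show.

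**Step 1. Can a subject be High at baseline?**
- ALT or AST: excluded at >= 1.5x ULN, so values above 1.0x and below 1.5x ULN can enter (Protocol 4.3, criterion 4).
- Total bilirubin: values above 1.0x and up to 1.5x ULN can enter under the direct-bilirubin condition (criterion 5).
- Stable fatty liver disease: the same 1.5x ALT/AST limit applies (criterion 7), so this adds no wider range.

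**Step 2. Is the entry value also the shift-table baseline?** SAP 11.3: "Baseline value is defined as the last non-missing value prior to the first dose of study drug". Protocol Table 1 and Section 7.2 schedule no Day 1 blood draw for clinical laboratory tests; the draws are at Screening, Weeks 4, 12 and 16, and Early Termination. The value that admitted the subject (or the single repeat allowed by Protocol 4.5) is therefore normally the baseline.

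**Step 3. Apply the mapping (7 indicators to 3 categories).**

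| Baseline | Post-baseline | Tabulated as | Shift shown? |
|---|---|---|---|
| Normal | High | Normal to High | yes |
| Normal | High Level 1 | Normal to High | yes, same cell |
| Normal | High Level 2 | Normal to High | yes, same cell |
| High | High Level 1 | High to High | no |
| High | High Level 2 | High to High | no |
| High Level 1 | High Level 2 | High to High | no |

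From a High-family baseline, 0 of 3 worsening moves show as a shift; with the alert levels kept separate, 3 of 3 would. From Normal, 3 different degrees of worsening fall in one cell. The Low side mirrors this.

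**Step 4. Illustration (assumed values).** ALT going from 1.4x to 8x ULN rises by 8 - 1.4 = 6.6x ULN and is tabulated High to High. ALT going from 0.95x to 1.05x ULN rises by 0.10x ULN and is tabulated as a shift. The documents do not give the alert cut-offs, but the first case is High to High whichever indicator 8x ULN receives.

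**Step 5. What the other planned outputs show.**

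| Output | Shows alert-level worsening? | Counts subjects by arm? |
|---|---|---|
| By-subject listings with indicators (SAP 12.9.3) | yes | no |
| Listing of markedly abnormal values (SAP 12.9.3) | perhaps; no laboratory threshold is given | no |
| Minimum, maximum and quartiles of values and changes (Protocol 10.4.3; SAP 11.1 without quartiles) | the extreme per visit and arm | no |
| TEAEs by maximum CTCAE grade (SAP 12.9.1) | only if the Investigator judges it clinically significant (Protocol 8.1.1) | yes |
| Shift tables (SAP 12.9.3) | no | yes, in three categories |

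By comparison, SAP 12.9.4 sets numeric limits for markedly abnormal change (for example 40 mmHg systolic, 30 bpm pulse) and calls for both a listing and a tabulation of those subjects.

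**The case against.** The strongest reply is that the endpoint concerns clinically significant change, and that such change already has a by-arm, graded table. Protocol 8.1.1 makes a laboratory abnormality an adverse event, including one that worsens from baseline, once the Investigator considers it clinically significant. SAP 12.9.1 then tabulates TEAEs by treatment and worst CTCAE grade. The descriptive summaries carry the maximum value and maximum change, so a single large rise is not buried in a mean. The listings keep every indicator. Movement across the reference range is also what a low/normal/high shift table is designed to show.

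Most of this stands. A reader might infer that alert-level worsening disappears from the report, or that the endpoint is not tabulated at all. The documents support neither.

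A reader might also assume that, say, 10% to 20% of subjects enter above ULN and conclude that 50 to 100 of 500 are affected (0.10 x 500 and 0.20 x 500). That does not follow. The documents give no such percentage. The calculation also counts everyone High at entry rather than those who then worsen on the same test, and a subject High on ALT can still show a shift on AST or bilirubin.

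What the reply does not answer is narrower. The adverse event route depends on individual judgment. The maximum flags one extreme without counting cases or showing where they started. Listings leave the counting to the reader. Protocol 10.4.3 provides in general terms for frequency tables of categorical safety data, but SAP 12.9.3 specifies none for the alert indicators.

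**Conclusion.** The point holds as a reporting gap. The shift tables cannot show worsening within the High or Low family and cannot grade worsening from Normal, and no other planned laboratory table counts alert-level worsening by arm. This follows from the mapping, the entry criteria and the baseline definition, and needs no numerical assumption.

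Its size in subjects cannot be computed: neither document defines Level 1 or Level 2 Alert or says how many subjects will enter above ULN. It affects no efficacy conclusion, no data collection and no monitoring of subjects during the trial. It is worth correcting because the affected tests include those tied to the nonclinical liver findings, and because the SAP already gives blood pressure and pulse the kind of tabulation that laboratory data lack.

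**What to change.** Amend SAP 12.9.3 in one of two ways:

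1. Keep the alert levels as separate shift-table categories, at least for ALT, AST and total bilirubin; or
2. Keep the three-category tables and add one table by arm with the number and percent of subjects whose worst post-baseline result reaches Level 1 or Level 2 Alert from a lower baseline category. Show it for all subjects and again for those above ULN at baseline on that test.

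In either case, cite the central laboratory's alert definitions in the SAP. A full seven-by-seven table for every test is not needed: it has 49 cells against 9, most of them likely to be empty.

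The cost is SAP wording, some programming, and somewhat wider or additional tables that will be sparsely filled. The central laboratory already supplies the indicators, so no new data are required and the change can be made before database lock.

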### 12.9.4 Vital Signs

Observed values and changes in vital sign parameters (systolic and diastolic blood pressure [SBP, DBP], pulse rate, and body temperature) will be summarized descriptively by visit and treatment group. Vital sign values will be classified as normal, low, high, based on reference ranges as per Table below. Subjects with markedly abnormal changes will be listed and tabulated separately.

	Absolute Values			Change (Absolute) from Baseline	
	Low	Normal	High	Abnormal Change	Markedly Abnormal Change
SBP	<90 mmHg	90-140 mmHg	>140 mmHg	≥ 20 mmHg	≥ 40 mmHg
DBP	<50 mmHg	50-90 mmHg	>90 mmHg	≥ 10 mmHg	≥ 20 mmHg
Pulse	<50 bpm	50-100 bpm	>100 bpm	≥ 10 bpm	≥ 30 bpm

### 12.9.5 Physical Examination

Brief physical examination results including weight, height, and BMI will be listed.

### 12.10 Pharmacokinetic Analyses

Plasma concentration data at Weeks 4 and 12 will be listed and summarized for the tapinarof cream, 1% group. Listings will be sorted by treatment, subject, day, and time.

The plasma concentrations divided by baseline total %BSA affected in cm^2 will be summarized descriptively as well. For this calculation, 1% BSA is equal to 185 cm^2.

Descriptive summaries will include n, mean, SD, median, minimum, and maximum. Concentration values below the limit of quantification will be treated as 0 in the summary.

In addition, plasma concentration at Weeks 4 and 12 will be summarized for the following subgroups:

- Age (<65 and ≥ 65 years old)
- Sex
- Race (White, Other)

Exploratory analyses may include relationships of plasma concentrations with patient demographics or AEs.

### **12.11 Additional Analyses - COVID-19**

In order to describe the impact of COVID-19 on current study, the following disposition events will be summarized in the tables separately:

- Subjects discontinued from the treatment/study as a result of a positive COVID-19 diagnosis.
- Subjects discontinued from the treatment/study due to other reasons related to COVID-19. This is excluding COVID-19 diagnosis but may include reasons such as site closure, travel restrictions, fear of infection, etc.
- Subjects with study visits altered (including modified in-clinic visit, virtual and phone visits) and missed due to COVID-19

COVID-19 related protocol deviations will be summarized separately. The impact of COVID-19 (including protocol deviation, visit alteration, treatment/study discontinuation and diagnosis of COVID-19) will also be flagged at subject-level in a data listing. Subject profile will be used to compile all COVID-19 related information for affected subjects.

An additional sensitivity analysis of the primary endpoint will be added in the ITT population based on OC only and excluding any virtual PGA assessments at Week 12.

Also, all COVID-19 related symptoms and confirmed cases occur during the study will be reported as AEs and included in the summaries.

## **13. CHANGES FROM THE PROTOCOL AND PLANNED ANALYSES**

The protocol specified change over time in physical component score and mental component score as measured by the SF-36 questionnaire as an exploratory endpoint. Scoring rules for the RAND 36-Item Health Survey (Version 1.0) are provided for the eight domain scores but not for the physical component score or the mental component score. Hence, summaries of the eight domain scores are planned.

No other changes from the protocol in planned analyses are noted. Any additional statistical analyses to handle modifications to study conduct and/or missing data due to the COVID-19 pandemic have been documented in Section 12.11 above in this SAP and will be finalized prior to database lock and unblinding of the study.

## **14. FORMATTING**

Each page of the analysis will show the sponsor's name, and the protocol number. Report tables will be embedded in the MS Word report document from SAS program output without change.

The footer of each table will show the name of the SAS program module which generated it and the date and time the table was generated.

The SAS programs will generate rich-text-formatted (RTF) output with the “RTF” extension using the SAS Output Delivery System (ODS). The summary tables and listings will be formatted using the Courier New 9-point font. The RTF output is included in report documents prepared with Microsoft Word and converted to PDF format without typographical change.

Datasets will be created and taken as input to validated SAS programs to generate the report-ready tables, listings, and figures. Each output display will show the names of the data sets and SAS program used to produce it.

## **15. ARCHIVING AND RETENTION OF DOCUMENTS**

After finalization of the analysis, the following will be archived at IQVIA Biotech and/or with the study sponsor:

- SAP and any amendments
- All SAS code used in the project for statistical analysis, report tables generation, and analysis data set creation
- Tables, listings and figures as included in the clinical study report
- SAS study data tabulation model (SDTM) and analysis dataset model (ADaM) datasets
